## 7.2 Pre-treatment

Within 28 days from C1D1:

- Sign written informed consent
- Medical history including prior cancer treatments, prior surgeries (requiring an overnight hospitalization), and pre-existing clinical signs and symptoms
- Record prior medications (taken within 30 days of C1D1)
- Complete physical exam
- Weight
- Vital signs (blood pressure, heart rate, respiratory rate, and temperature)
- ECG (a standard 12-lead ECG in triplicate, approximately 2 to 5 minutes apart) is taken while patient is in a semi-recumbent position
- Imaging for tumor measurements by RECIST 1.1 ([APPENDIX II](#))
- Confirmation of eligibility

Within 7 days from C1D1:

- ECOG performance status ([APPENDIX I](#))
- Blood draw for hematology
- Blood draw for serum chemistry
- Pregnancy test for women of childbearing potential

## 7.3 During Treatment

### 7.3.1 Day 1 of Cycle 1

- Eligibility must be re-verified before dosing on Day 1
- Physical exam (may be done within 3 days prior)
- Weight (may be done within 3 days prior)
- Vital signs (blood pressure, heart rate, respiratory rate, and temperature) at 3 timepoints: pre-dose, at 30 min ( $\pm 5$  min), and at 1hr ( $\pm 5$  min) after end of PTX-35 infusion
- ECG (a standard 12-lead ECG in triplicate, approximately 2 to 5 minutes apart) taken while patient is in a semi-recumbent position (may be done within 3 days prior)
- ECOG performance status (may be done within 3 days prior)
- Blood draw for hematology (may be done within 3 days prior)
- Blood draw for serum chemistry tests (may be done within 3 days prior)
- Blood sample for pharmacokinetics at 4 timepoints: pre-dose; 30min ( $\pm 5$  min), 2hr ( $\pm 5$  min) and 4hr ( $\pm 5$  min) after end of PTX-35 infusion
- Blood sample for cytokines at 2 timepoints: pre-dose, and 2hr ( $\pm 5$  minutes) after end of PTX-35 infusion
- Blood sample for anti-therapeutic antibodies (ATA) and anti-TENIVAC antibody titer (pre-dose)
- Blood sample for immunological effect (pre-dose)

- Blood sample for HLA (pre-dose)
- PTX-35 administration and observation period
- TENIVAC administration
- Concomitant medications review
- Adverse event assessment

### **7.3.2 Days 2, 4, 7, and 10 of Cycle 1 and Cycle 2**

- Blood sample for pharmacokinetics at the following post-dose time points:  
Day 2 - 24hr ( $\pm 2$ hr), Day 4 – 72hr ( $\pm 2$ hr), Day 7 – 144hr ( $\pm 2$ hr) and Day 10 – 216hr ( $\pm 2$ hr)
- Blood sample for immunological effect (Day 7 only)
- Concomitant medications review
- Adverse event assessment

### **7.3.3 Day 1 of Cycle 2 (+ 2 days)**

- Physical exam
- Weight
- Vital signs (blood pressure, heart rate, respiratory rate, and temperature): pre-dose; 30 min ( $\pm 5$  min) and 1hr ( $\pm 5$  min) after end of PTX-35 infusion
- ECG (a standard 12-lead ECG in triplicate (approximately 2 to 5 minutes apart) taken while patient is in a semi-recumbent position
- ECOG Performance status
- Blood draw for hematology
- Blood draw for serum chemistry tests
- Blood sample for pharmacokinetics at 4 timepoints: pre-dose; 30min ( $\pm 5$  min), 2hr ( $\pm 5$  min) and 4hr ( $\pm 5$  min) after end of PTX-35 infusion
- Blood sample for cytokines at 2 time points: pre-dose and 2hr ( $\pm 5$  min) after end of PTX-35 infusion
- Blood sample for anti-therapeutic antibodies (ATA) and anti-TENIVAC antibody titer (pre-dose)
- Blood sample for immunological effect (pre-dose)
- PTX-35 administration and observation period
- Concomitant medications review
- Adverse event assessment

### **7.3.4 Day 1 of Cycle 3 and Beyond (+ 2 days)**

- Physical exam
- Weight
- Vital signs (blood pressure, heart rate, respiratory rate, and temperature): prior to PTX-35 infusion

- ECG (a standard 12-lead ECG in triplicate, approximately 2 to 5 minutes apart) taken while patient is in a semi-recumbent position
- ECOG Performance status
- Blood draw for hematology
- Blood draw for serum chemistry tests
- Blood draw for pharmacokinetics (C3D1 pre-dose only)
- Blood sample for cytokines (ONLY IF PATIENT IS SYMPTOMATIC) at 2 time points: pre-dose and 2hr ( $\pm 5$  min) after end of PTX-35 infusion
- Blood sample for anti-therapeutic antibodies (ATA) and anti-TENIVAC antibody titer (pre-dose)
- PTX-35 administration and observation period
- Concomitant medications review
- Adverse event assessment
- Imaging for tumor measurements by RECIST 1.1 via CT scans or MRI (every 8 weeks  $\pm 1$  week from C1D1 until disease progression)

#### **7.4 30-Day Safety Follow up Visit**

The following assessments will be performed at 30 days  $\pm 3$  days of the last administration of PTX-35 for all patients who are off study treatment:

- Physical exam
- Weight
- Vital signs (blood pressure, heart rate, respiratory rate, and temperature)
- ECOG Performance status
- Blood draw for hematology
- Blood draw for serum chemistry tests
- Blood draw for immunological effect
- Blood sample for anti-therapeutic antibodies (ATA) and anti-TENIVAC antibody titer
- Concomitant medications review
- Adverse event assessment

#### **7.5 Post-Treatment Follow-Up**

Any patient that stops treatment (or starts new anti-cancer treatment) for any reason other than progressive disease will enter the Post-Treatment Follow-Up period, which refers to the time between last dose of PTX-35 and disease progression. The following assessments will be performed every 8 weeks from the date of last scan ( $\pm 1$  week) during the Post-Treatment Follow-Up period:

- Imaging for RECIST 1.1 tumor measurements via CT scan or MRI every 8 weeks ( $\pm 1$  week)
- Concomitant medications review, limited to subsequent anti-cancer therapy

- Adverse event assessment (only if deemed related to PTX-35)

## 7.6 Survival Follow-up

The Survival Follow-Up period refers to the time between disease progression (or initiation of anti-cancer treatment) and patient death. Survival status and subsequent anti-cancer therapy will be collected approximately every 12 weeks in a clinic visit, or by telephone/electronic communication. Patients who withdraw consent for study procedures should still be followed for survival and/or public records searched as per FDA guidance issued October 2008 entitled "Guidance for Sponsors, Clinical Investigators, and IRBs: Data Retention When Subjects Withdraw from FDA-Regulated Clinical Trials".

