- n. Pre-dose blood sample collection to monitor development of anti-therapeutic antibodies (ATA) and anti-TENIVAC antibody titer.
- o. Blood sample collection for immunological effect; Day 1 (prior to PTX-35 administration) and Day 7 for Cycle 1 and Cycle 2, and 30-Day Safety Follow-Up only.
- p. In post-treatment and survival follow-up, concomitant medications limited to subsequent anti-cancer therapy.
- q. If  $> 30$  days since last dose, only record AEs if deemed related to Investigational Product
- r. Survival status and subsequent anti-cancer therapy information will be collected approximately every 12 weeks in a clinic visit or by telephone/electronic communication, from the time of disease progression or initiation of new anti-cancer treatment until death.

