Adverse events will be followed until resolution or stabilization while the patient remains on-study. Once the patient is removed from study, events thought to be related to the Investigational Product will be followed until resolution or stabilization, unless, in the Investigator's opinion the event is unlikely to resolve due to the patient's underlying disease, or until the patient starts a new treatment regimen or the patient is lost to follow-up.

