### **9.3 Safety**

Safety will be assessed throughout the study by means of physical examination, weight, vital signs, ECOG performance status, laboratory evaluations (hematology, biochemistry and cytokines), electrocardiogram (ECG), and recording of concurrent illness/therapy and treatment-emergent adverse events. CTCAE version 5.0 will be used to grade all toxicities. All related adverse events will be monitored until resolution or permanent outcome. Concomitant medications will be recorded throughout the study.

Cytokines will be monitored during cycle 1 and 2. Patients will also be monitored for any clinical symptoms associated with elevated cytokine levels. Cytokines will only be monitored at cycle 3 and beyond if patient is symptomatic (i.e., flu-like symptoms, fever, or allergic reactions).

Safety data will be summarized for the safety evaluable population. These data will include Treatment emergent adverse events (TEAEs) and laboratory parameters. Adverse event terms will be coded using the most current version of Medical Dictionary for Drug Regulatory Activities (MedDRA).

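### After the 30-day visit, related adverse events are scheduled to be asked about only in patients who stopped without progression, so late related events may be under-ascertained after progression; the follow-up rules also need reconciling

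*Combined protocol and SAP*

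**What the plan says.** Section 7.4 gives every patient a visit about 30 days after the last dose, "for all patients who are off study treatment", and that visit includes an AE assessment. The routes then divide.

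- **Section 7.5.** A patient who stops "for any reason other than progressive disease will enter the Post-Treatment Follow-Up period", which lasts until progression. The eight-weekly list there includes "Adverse event assessment (only if deemed related to PTX-35").
- **Section 7.6.** "The Survival Follow-Up period refers to the time between disease progression (or initiation of anti-cancer treatment) and patient death". What is gathered is stated in one sentence: "Survival status and subsequent anti-cancer therapy will be collected approximately every 12 weeks in a clinic visit, or by telephone/electronic communication". No adverse event item is listed.
- **Table 2, footnote q.** More than 30 days after the last dose, sites are to "only record AEs if deemed related to Investigational Product". Progression is not mentioned.
- **Section 8.1.2.6.** A related SAE occurring later than 30 days after the last dose must be notified within 24 hours of awareness. There is no time limit and no progression limit.

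There are two rules for related events that are already known. Section 8.1.2.1 says that, once the patient is off study, follow-up runs to resolution or stabilization, with exceptions that include "or until the patient starts a new treatment regimen or the patient is lost to follow-up". Section 9.3, with the same sentence in the synopsis, says: "All related adverse events will be monitored until resolution or permanent outcome".

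**The concern.** One of the two primary endpoints (9.2.1) is the frequency of PTX-35-related TEAEs and SAEs during the trial, and no closing date is given for the TEAE window. The plan clearly means to capture related events beyond 30 days, since footnote q and 8.1.2.6 both provide for them. Yet whether anyone asks about such events depends on why the patient stopped. If the share stopping for progression differs between dose levels, late-event capture could differ between dose levels too. The documents hold no data on whether it would.

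This is a first-in-human study, and section 6.1.3 says that events after the four-week DLT window will be reviewed across cohorts to help inform escalation. The part at risk is narrow: events that first appear after the 30-day visit in patients who have progressed. Events on treatment and up to the 30-day visit are collected in every patient.

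The conflict between 8.1.2.1 and 9.3 is a separate matter. It affects the recorded outcome and duration of known related events, and a site cannot satisfy both rules when a patient with an open related event moves to a new regimen.

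**Working it through.** The plan states no figure on this point, so the check is mainly a comparison of sections.

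**1. Scheduled AE questions after the last dose**

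| Patient | 30-day visit (7.4) | Afterwards |
|---|---|---|
| Stopped without progression, no new therapy | AE assessment | Related AEs every 8 weeks (7.5) until progression, then 7.6 |
| Stopped for progression | AE assessment | 7.6 only: vital status and next therapy, about every 12 weeks |
| Started new therapy without progression | AE assessment | Named in both 7.5 and 7.6 (and footnote r): schedule undefined |

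Patients treated beyond radiological progression (8.2.1) keep their AE assessment at each cycle (7.3.4), so for them the gap begins later.

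**2. Could another provision supply the missing question?**

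- 8.1.2.6 is triggered by awareness, and only for serious events.
- Footnote q permits recording but does not create a contact.
- 8.1.2.1 asks for a non-directed interview at each evaluation, but does not say that a telephone or electronic survival contact is an evaluation.
- In Table 2, as its columns come through in the text available for review, the AE mark (q) and the survival mark (r) stand in the same last follow-up column. A column heading may have been lost, so the table does not settle the matter. If the intact table does mark AE assessment at survival contacts, then it disagrees with 7.6.

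**3. Follow-up of known related events**

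Take a patient who is off study, has an unresolved related event and starts next-line therapy. Under 8.1.2.1 follow-up may end. Under 9.3 and the synopsis it continues until the event has resolved or is permanent. The two cannot both be applied. This conflict concerns events already recorded, so it does not affect detection of new ones.

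**4. Scale, for illustration only**

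Inputs: planned N of 22–34 (9.8); share stopping for progression 50–90% (assumed); risk of a late related event 2%, 5% or 10% per patient (assumed).

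Patients with no scheduled late-AE question, m = N × share:

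- low: 22 × 0.5 = 11
- high: 34 × 0.9 = 30.6, or 31

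Expected events = m × p. Chance of at least one = 1 − (1 − p)^m.

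| p | Expected, m = 11 to 31 | At least one, m = 11 to 31 |
|---|---|---|
| 2% | 0.22 to 0.62 | 20% to 47% |
| 5% | 0.55 to 1.55 | 43% to 80% |
| 10% | 1.1 to 3.1 | 69% to 96% |

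These are late related events of any seriousness that could arise in the group. They are not events missed, because some would reach the site unprompted.

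**The case against.** The strongest reply is that the plan is not silent on late events. Related SAEs are reportable at any time, footnote q lets related AEs be recorded after 30 days whatever the reason for stopping, and Table 2 may already mark an AE assessment during survival follow-up. All of this stands, and it rules out saying that late non-serious events have no route into the database. What remains is that 7.6 schedules no question to elicit them.

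A reader might infer more than the documents support:

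- **That late immune toxicity is missed in many patients.** The documents give neither a late-event rate nor a progression share, and the absence of a scheduled question is not a missed event. Section 2.6 describes the immune-related risk as apparently limited.
- **That section 8.2.1 warns of delayed toxicity.** Its remark on delayed immune effects is there to justify treatment beyond progression for possible benefit, so it is about antitumor response.
- **That the 30-day visit is too early.** At the monkey half-life of 163 h (2.4.2), 30 days is 720/163 = 4.42 half-lives, leaving 0.5^4.42 = 4.7% of drug if that half-life held in humans. This does not show the visit to be badly timed. The six-month contraception period is a reproductive precaution and does not show it either.
- **That the 8.1.2.1 conflict causes events to go undetected.** It governs known events only. Its cut-off applies once a patient is off study, and whether survival follow-up counts as off study is not defined.

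It is also fair to say that asking about related events after new therapy begins gives answers that are harder to attribute. That is a real but modest cost.

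**Conclusion.** The point holds in a limited form. After the 30-day visit, the visit sections schedule solicitation of related events only for patients who stopped without progression, and only until they progress. Under-ascertainment after progression is therefore possible for late non-serious related events and for serious ones the site does not learn of.

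Its size cannot be derived from the documents. Under the assumed 50–90% progression share, 11–31 of 22–34 patients would lack a scheduled question. Under the assumed risks, expected late events in that group run from below one to about three. Any unevenness between dose levels is a possibility, with no figure behind it.

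Two inconsistencies in the text hold without any assumption: 8.1.2.1 against 9.3 and the synopsis on when follow-up of a known related event ends, and 7.5 against 7.6 on patients who start new therapy without progression. The change is worth making because it is cheap and serves a primary endpoint the plan already means to measure beyond 30 days.

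**What to change.** 1. In 7.6 and Table 2, add to the existing 12-weekly contact: any related AE or SAE since last contact, and the outcome of any open related AE. Make the Table 2 columns and footnote q agree with the text.
2. Record the start date of new anti-cancer therapy as a flag, so that analysts can separate events before and after it.
3. Reconcile 8.1.2.1 with 9.3 and the synopsis into one rule for how long a known related event is followed, and say whether a patient in survival follow-up counts as on study.
4. State which follow-up period, and hence which AE schedule, applies to a patient who starts new therapy without progression.

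The cost is one question and one CRF line at a contact that already takes place, plus a wording amendment. The downside is harder attribution once a new therapy has begun. The date flag helps with this but does not remove it.

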## 8.0 STUDY ASSESSMENTS

### 8.1 Safety Assessments

#### 8.1.1 Safety Analysis

Safety data will be summarized for the safety evaluable population. These data will include Treatment emergent adverse events (TEAEs) and laboratory parameters. Adverse event terms will be coded using the most current version of Medical Dictionary for Drug Regulatory Activities (MedDRA).

#### 8.1.2 Reporting of Adverse Events

##### 8.1.2.1 Adverse Events

An adverse event (AE) is any untoward medical occurrence in a patient or clinical investigation subject administered a pharmaceutical product that does not necessarily have a causal relationship with the treatment. An adverse event can be any unfavorable and unintended sign (including a laboratory finding), symptom or disease temporally associated with the use of an Investigational Product, whether or not related to the Investigational Product.

The AE reporting period starts on Cycle 1 Day 1 after the first dose of PTX-35. If an AE occurs before the first dose of study drug it will be captured as baseline and considered part of medical history unless it directly related to a study procedure (in which case it may be reported as an AE). At each evaluation, patients should be interviewed in a non-directed manner to elicit potential adverse reactions from the patient. The occurrence of an adverse event will be based on changes in the patient's physical examination, laboratory results, and/or signs and symptoms.

All adverse events (except Grade 1 and 2 laboratory abnormalities that do not require an intervention), regardless of causal relationship, are to be recorded in the case report form and source documentation. The Investigator must determine the intensity of any adverse events according to the NCI Common Terminology Criteria for Adverse Events (CTCAE) version 5.0 and their causal relationship. Those AEs not covered by these criteria will be graded as follows:

1. Mild: Discomfort noticed, but no disruption of normal daily activity. Prescription drug not ordinarily needed for relief of symptom but may be given because of personality of patient.
2. Moderate: Discomfort sufficient to reduce or affect normal daily activity. Patient is able to continue in study; treatment for symptom may be needed.
3. Severe: Incapacitating, severe discomfort with inability to work or to perform normal daily activity. Severity may cause cessation of treatment with test drug; treatment for symptom may be given and/or patient hospitalized.
4. Life-Threatening: Symptom(s) place the patient at immediate risk of death from the reaction as it occurred; it does not include a reaction that, had it occurred in a more serious form, might have caused death.
5. Fatal: Event caused the death of the patient.

Adverse events will be followed until resolution or stabilization while the patient remains on-study. Once the patient is removed from study, events thought to be related to the Investigational Product will be followed until resolution or stabilization, unless, in the Investigator's opinion the event is unlikely to resolve due to the patient's underlying disease, or until the patient starts a new treatment regimen or the patient is lost to follow-up.

### **8.1.2.2 Attribution Definitions**

An adverse event is considered to be associated with the use of the Investigational Product if the attribution is determined as possible or definite. Attribution of AEs will be recorded in the CRF as:

- Unrelated: The AE is clearly *not* related to the study treatment.
- Possible: The AE may be related to the study treatment.
- Definite: The AE is clearly related to the study treatment.

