### 4.2 Overview of Trial Design

This is an open-label, single arm, first-in-human, Phase I study of the intravenous administration of PTX-35 to patients with advanced solid tumors refractory to, or ineligible for, or who refuse, SOC therapy.

Patients who meet the eligibility criteria will be enrolled to receive intravenous PTX-35 every two weeks as well as a single intramuscular injection of TENIVAC vaccine on Day 1 of Cycle 1. Upon completion of two cycles of PTX-35, in the absence of disease progression or unacceptable toxicity, patients may continue to be treated with PTX-35 at the same dose and schedule until disease progression, death, and patient withdrawal of consent, Investigator's decision to remove patient, or intolerable toxicity, whichever occurs first. At the discretion of the Investigator, and in the absence of clinical deterioration, treatment with PTX-35 may continue beyond initial evidence of radiological progression as per Section 8.2.1.

Seven escalating dose levels of PTX-35 will be explored using a traditional 3+3 design based on DLTs (dose-limiting toxicities) until optimal immunological dose (OID) or maximum tolerated dose (MTD) is established. The starting dose of PTX-35 is based on the MABEL for Treg activity (considered the most sensitive of PTX-35 pharmacodynamic markers) obtained from dose-ranging studies conducted in non-clinical animal models. PTX-35 will be administered to patients intravenously on Day 1 of each cycle. The length of each cycle is 14 days, and the DLT period includes the safety data obtained from the first two treatment cycles (4 weeks).

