#### **6.1.1.2 TENIVAC Vaccine**

TENIVAC vaccine is a suspension available in 0.5 mL single-dose for injection. TENIVAC vaccine is a sterile isotonic suspension of tetanus and diphtheria toxoids adsorbed on aluminum phosphate. Each 0.5 mL dose of TENIVAC vaccine contains the following active ingredients: Tetanus Toxoid 5 Lf (flocculation units) and Diphtheria Toxoid 2 Lf. Other ingredients per 0.5 mL dose include 1.5 mg of aluminum phosphate (0.33 mg of aluminum) as the adjuvant and ≤5.0 mcg of residual formaldehyde.

TENIVAC will be administered via intramuscular injection on Day 1 of Cycle 1 only and will be administered per the current product package insert.

If any serious adverse reaction occurs these may be treated per institutional practice, as noted in Section [6.4 Concomitant Treatment](#).

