#### **6.1.2 Dose Escalation Scheme**

Escalating doses of PTX-35 will be administered to patients via intravenous infusion on Day 1 of each cycle.

Upon completion of two cycles (4 weeks), in the absence of disease progression or unacceptable toxicity, patients may continue to be treated with PTX-35 at the same dose and schedule until disease progression, death, and patient withdrawal of consent, Investigator's decision to remove patient, or intolerable toxicity, whichever occurs first. At the discretion of the Investigator, treatment with PTX-35 may continue beyond initial evidence of radiological progression as per Section [8.2.1](#).

Seven escalating dose levels of PTX-35 will be explored using a traditional 3+3 design based on DLTs (dose-limiting toxicities) until MTD (maximum tolerated dose) or optimal immunological dose (OID) is established. The starting dose of PTX-35 is based on the MABEL for Treg activity (considered the most sensitive of PTX-35 pharmacodynamic markers) obtained from dose-ranging studies conducted in non-clinical animal models. PTX-35 will be administered to patients intravenously on Day 1 of each cycle. The length of each cycle is

14 days, and the DLT observation period includes the safety data obtained from the first two treatment cycles (4 weeks).

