#### DLT excludes:

- Hematological and non-hematological  $\leq$  Grade 2 unless considered non-acceptable.
- Other Grade 3 self-limited or medically controllable toxicities (e.g., fever without  $\geq$  Grade 3 neutropenia, lymphopenia, nausea, vomiting, diarrhea, fatigue). Note, such events are considered DLT if the abnormality leads to hospitalization or the abnormality persists for  $>72$  hours despite appropriate interventions (e.g., replacement therapy for electrolyte abnormalities, when indicated).
- Electrolyte disturbances that are managed to Grade 1 or less with supplemental therapy.

Any adverse event that is potentially related to PTX-35 and requires discontinuation of treatment should be considered a DLT. A DLT will be considered related to PTX-35 treatment unless there is a clear, well-documented relation to intercurrent illness or primary malignant disease. AEs that meet the above criteria but occur after the DLT evaluation period will not be defined as DLTs but will be reported as AEs/Serious Adverse Events (SAEs), as applicable, and will be reviewed across all cohorts during the study to help inform dose escalation decisions.

In case of suspicion of a DLT, the Investigator must inform the Medical Monitor/Sponsor immediately. The DLT will be confirmed by the Medical Monitor/Sponsor and a decision must be taken by the Sponsor regarding if an *ad hoc* SRC meeting is required.

Patients who discontinue therapy before completion of 2 cycles (DLT period) for other reasons than dose-limiting toxicity will be replaced. Patients who are tolerating PTX-35 will not have to discontinue study treatment prematurely due to the occurrence of DLTs in another patient in the same cohort, unless decided by the SRC.

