## 9.2 Endpoints

### 9.2.1 Primary

- Number of Dose-limiting toxicities (DLTs) per NCI CTCAE v5.0.
- Frequency of treatment-emergent adverse events (TEAEs) and serious adverse events (SAEs) related to PTX-35 during the trial.

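### A single causality scale against an undefined study treatment does not reliably keep TENIVAC-only reactions out of the primary endpoint of PTX-35-related events

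*Combined protocol and SAP*

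**What the plan says.** Two products are given on the same day. Section 4.2 has patients receive intravenous PTX-35 every two weeks "as well as a single intramuscular injection of TENIVAC vaccine on Day 1 of Cycle 1". Section 6.1.1.2 confirms the vaccine timing ("TENIVAC will be administered via intramuscular injection on Day 1 of Cycle 1 only") and Section 6.1.2 the antibody timing ("PTX-35 will be administered to patients intravenously on Day 1 of each cycle").

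Section 8.1.2.2 sets out one three-level attribution to be recorded in the CRF: unrelated, possible or definite. Each level refers to the study treatment; possible, for example, means "The AE may be related to the study treatment". The same section then converts the scale: "An adverse event is considered to be associated with the use of the Investigational Product if the attribution is determined as possible or definite".

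The second of the two primary endpoints in Section 9.2.1 is specific to one product: "Frequency of treatment-emergent adverse events (TEAEs) and serious adverse events (SAEs) related to PTX-35 during the trial". No section describes a causality assessment for TENIVAC, says how expected vaccine reactions are to be coded, or says how relation to PTX-35 is derived from the single scale.

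**The concern.** The endpoint names PTX-35, while the scale that feeds it names study treatment. If an investigator takes study treatment to mean everything the protocol administers, a reaction caused by the vaccine alone is possible or definite and enters the PTX-35-related count. If another investigator takes it to mean PTX-35, the same reaction can be unrelated. All analyses are descriptive and presented by dose level, so the table of related events by dose is itself the result; no test or model later corrects a misclassification. Every patient at every dose level is vaccinated, so no vaccine-free group shows the background rate.

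**Working it through.** The plan states no vaccine reaction rate and performs no sample size calculation, so there is no figure to reproduce. The check is of wording first, then an illustration under assumed rates.

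**Step 1: what the two terms cover.**

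| Reading | Where |
|---|---|
| PTX-35 only | Section 2.2 is headed as the investigational product and covers PTX-35; TENIVAC has its own Section 2.3 |
| PTX-35 only | Table 2 footnote q limits late AEs to those related to the Investigational Product; Section 7.5 gives the same limit in terms of PTX-35 |
| PTX-35 only | Sections 6.1.3 and 6.2 use study treatment for continued or resumed PTX-35 dosing |
| Both products | The synopsis describes TENIVAC under its test product heading |
| Both products | TENIVAC is Section 6.1.1.2, under the Section 6.1 heading on investigational product preparation and the Section 6.1.1 heading on drug products |
| Open | Section 5.5 uses a further undefined term, study agent(s) |

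The narrow reading is the more common one, but neither is excluded. Even on the narrow reading, unrelated requires that the event is clearly not related. Fever on the shared day, which Section 6.3 also lists as a sign of an infusion reaction, would naturally be coded possible.

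**Step 2: size under assumed rates.** Read frequency as the share of patients with at least one related event. Let q be the true PTX-35-related share and v the share with a vaccine-only event that is scored as related, taken as independent.

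- Recorded share = 1 − (1−v)(1−q)
- Inflation = recorded share − q = v(1−q)

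| Assumed v | q = 0% | q = 10% | q = 30% |
|---|---|---|---|
| 5% | 5% | 14.5% | 33.5% |
| 20% | 20% | 28% | 44% |
| 40% | 40% | 46% | 58% |
| 60% | 60% | 64% | 72% |

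The inflation is not constant. At v = 60% it is 60 points when q = 0 and 0.6 × 0.7 = 42 points when q = 30%. A true difference between dose levels shrinks by the factor (1−v): at v = 40%, a true 30-point difference reads 58 − 40 = 18 points.

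Here v counts only vaccine-only events that are actually scored as related. The rows from 20% to 60% are an upper-end illustration: if they are taken as vaccine reaction rates, every reaction would have to be counted against PTX-35.

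**Step 3: Grade 3 vaccine reactions in a cohort of three.** With an assumed per-patient rate r, the chance of at least one is 1 − (1−r)³:

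- r = 1%: 3.0%
- r = 3%: 8.7%
- r = 5%: 14.3%

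These are chances of a Grade 3 vaccine reaction, not of a DLT. Section 6.1.3 excludes self-limited or medically controllable Grade 3 events unless they lead to hospitalization or last more than 72 hours, and the Medical Monitor/Sponsor confirms each DLT.

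**The case against.** The strongest reply is that the protocol mostly uses both terms for PTX-35, so a plain vaccine reaction such as pain at the intramuscular site would be coded unrelated and never reach the endpoint. This stands in part. A reader might infer from Section 8.1.2.2 that the endpoint necessarily counts vaccine reactions; the documents show only that it can. They also leave room for two readings of a primary endpoint.

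Three further replies carry weight.

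- Section 2.3 includes TENIVAC partly to study the safety of PTX-35 when the immune system is activated. A vaccine reaction amplified by PTX-35 belongs in the PTX-35 safety profile. It also means that v may vary with dose, so the independence assumption is only a convenience.
- Some separation is possible afterwards. The vaccine is given once and PTX-35 every 14 days, events are MedDRA-coded, and all data are listed. But this does not recover what the investigator judged about a Cycle 1 event.
- The direction is conservative in an exploratory first-in-human trial, and the CRF itself is not among the documents; that it holds a single field is inferred from Section 8.1.2.2.

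Section 6.1.3 might seem to extend the problem to DLTs, since "A DLT will be considered related to PTX-35 treatment unless there is a clear, well-documented relation to intercurrent illness or primary malignant disease" does not list the vaccine as an alternative cause. That presumption is deliberately cautious, and the documents give no basis for a rate of vaccine-driven DLTs.

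**Conclusion.** The point holds as a gap in definition and recording. The endpoint of related TEAEs and SAEs can count vaccine-only reactions, sites may code them differently, and one scale does not reliably separate them.

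The size is unknown. Under the stated assumptions the inflation is v(1−q), largest where true PTX-35 toxicity is lowest, which would be the lowest dose levels if toxicity rises with dose. A reader might infer a fixed bias of 20 to 60 points, a hidden dose-response, or a 3–14% chance of a vaccine-driven DLT in a cohort of three. The documents support none of these: the first needs every vaccine reaction to be counted and q to be zero, the second depends on an unknown v that may itself change with dose, and the third is not a DLT rate. This is a worthwhile, inexpensive improvement; it is not evidence that the trial's safety result will be wrong.

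**What to change.** - Define study treatment and Investigational Product in Section 8.1.2.2 and use them consistently.
- Record two causality judgements for each AE and SAE, one for PTX-35 and one for TENIVAC, on the existing three-level scale.
- State in Section 9.2.1 that related events are those with possible or definite relation in the PTX-35 field. Ambiguous reactions, and those thought to be amplified by PTX-35, then still count.
- Tabulate TENIVAC-only events separately by dose level.
- Leave the DLT relatedness rule as it is, and show both attributions to the Safety Review Committee.

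The cost is one CRF field, a few sentences and one more investigator judgement per event. Sample size, dose and schedule do not change. The gain is limited to events clearly caused by the vaccine, because ambiguous systemic events will remain possible for both products.
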